# **Definition:**

This endpoint is defined as the value at V7 in the response to treatment (based on PGO-C).

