	- Changes in the average number of cataplexy episodes per were (recorded in sleep diary by patient and/or parent/teacher) between the weeks of baseline and the 2 weeks of end study treatment period (VV7), in pitolisant and placebo groups.						
Main secondary	- Differences in weekly frequency of cataplexy episodes (recorded in sleep diary by patient and/or parent/teacher) between baseline and the 4 weeks of stable treatment period (V4 to V7), in pitolisant and placebo groups.						
endpoint(s) with time(s) of assessment	- Severity of EDS measured by the Clinical Global Impression of severit and change. Changes between baseline and V6, V7, in pitolisant an placebo groups.						
	- Severity of cataplexy measured by the Clinical Global Impression of severity and change. Changes between baseline and V6, V7, in pitolisant and placebo groups.						
	- Changes between baseline and V6 will be compared for the TEA-Ch test, in pitolisant and placebo groups.						
	- Comparison between placebo and pitolisant groups on:						
	- Withdrawal symptoms questionnaire (DSM IV)						
	 Patients' Global Opinion on treatment effect at the end of treatment if able to express himself. If not will be reported either by parents or teachers. 						
	- Changes between baseline and at each visit of the open-label period in EDS.						
	- Safety assessment will be done on monitoring of adverse events, physical examination, vital signs, ECG and Blood Laboratory tests modifications and the mood appraisal throughout the study.						
A41 1	Double-blind period:						
Authorized treatments	If Patients are treated with sodium oxybate, a stable dosage is required for a minimum period of 4 weeks prior to inclusion (V2), and this dosage should be maintained stable throughout the study.						

EudraCT number: 2013-00	1506-29

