- Global opinion on the effect of investigational treatment will be reported by patient if able to express himself. If not will be reported either by parents or teachers.
- Investigational treatment allocation: start 1-week wash-out period.

T1 - Telephone contact at D59 (± 1 day)

During this telephone contact, the investigator should:

- Ascertain that the treatment discontinuation is well tolerated
- Record all adverse events that have occurred
- Withdrawal symptoms questionnaire

V8 - End of study visit after 1 week of placebo wash out or (D63 \pm 2 days) / Start of Open label or Premature withdrawal visit (within 5 days after last treatment intake)

The premature withdrawal patients should be followed by a visit performed within a maximum of 5 days after the last dose of study drug.

- A complete interrogation including control of the treatment compliance, count of remaining tablets and verification of the forgotten treatment intake.
- Adverse events and concomitant medication recording,
- A physical examination including vital signs shall be carried out,
- 12-lead ECG (QTcF value),
- A blood sample will be taken for routine haematological and biochemical test (including β -HCG pregnancy test for pubescent female) and semi-quantitative urinalysis (dipstick). (only for premature withdrawal patients),
- The following questionnaires should be performed:
 - PDSS.
 - CASS.
 - UNS (only for premature withdrawal patients),
 - CGI-C on EDS and on cataplexy,
 - CDI,
 - C-SSRS.
 - -Global opinion on the effect of investigational treatment will be reported by patient if able to express himself. If not will be reported either by parents or teachers. (only for premature withdrawal patients),
 - Retrieval of sleep diary.
 - -Withdrawal symptoms questionnaires.

Patients willing to continue the study in the prolonged open label period will receive a new pack of investigational treatment and will start an escalating dose treatment. Those patients will receive one sleep diary which have to be filled out daily during the 7 days prior to the next visit. Patients not willing to continue in the study will be followed under usual practice.

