3.3.2. Secondary endpoints

As secondary endpoints the study will assess efficacy and safety endpoints in pitolisant and placebo groups:

- Changes in EDS as measured by the maintenance of wakefulness test (MWT) between baseline and V7,
- Changes in EDS measured by the Paediatric Daytime Sleepiness Scale (PDSS) between baseline: [V1 score (D-14) + V2 score (D0)]/2 and the end of treatment: [V6 score (D49) + V7 score (D56)]/2,
- Changes in EDS as measured by the Child and Adolescent Sleepiness Scale (CASS) between baseline and the end of treatment.
- Changes in the average number of cataplexy episodes per weeks: (recorded in sleep diary by patient and/or parent/teacher) between the 2 weeks of baseline and the 2 weeks of end study treatment period (V6, V7),
- Differences in weekly frequency of cataplexy episodes (recorded in sleep diary by patient and/or parent/teacher) between baseline and the 4 weeks of stable treatment period (V4 to V7),
- Severity of EDS measured by the clinical Global Impression of severity and change. Changes between baseline and V6, V7,
- Severity of cataplexy measured by the clinical Global Impression of severity and change. Changes between baseline and V6, V7,
- Changes between baseline and V6 will be compared for the TEA-Ch test,
- Comparison between placebo and pitolisant groups on:
 - Withdrawal symptoms questionnaire (DSM IV) on D59 during a phone call (T1) and at the end-of-study visit on D63 (V8) after a one-week period on placebo,
 - Patients' Global Opinion on treatment effect at the end of treatment if able to express

Protocol P11-06/ BF2.649 EudraCT number: 2013-001506-29

himself. If not will be reported either by parents or teachers.

- ,Tolerability as measured by Treatment Emergent Adverse Events (TEAE),
- Changes in Physical examination and Vital signs,
- ECG and calculation of Fridericia's corrected QTc interval (QTcF = $QT/\sqrt{3}\sqrt{60/HR}$),
- Blood laboratory tests (haematology, blood chemistry),
- Mood appraisal adapted to children (CDI and C-SSRS).
- Changes between baseline and at each visit of the open-label period in EDS,
- Safety assessment will be done on monitoring of adverse events, physical examination, vital signs, ECG and Blood Laboratory tests modifications and the mood appraisal throughout the study.

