3.7.1.2.7. Patient's Global Opinion on the effect of treatment

At V7 and all visits of open-label period, patients' global opinion will be reported by patient if able to express himself. If not, either their parents or their main teachers should evaluate the Global effect of the treatment by comparing the period prior to that visit with the patient's prestudy condition.

The following six-level scale will be used:

- Marked effect (complete or nearly complete remission of EDS)
- Moderate effect (partial remission of EDS)
- Minimal effect (slight decrease in EDS that does not substantially alter the status of the patient)
- No change
- Minimally worse (slight increase in EDS)
- Much worse (substantial increase in EDS)

3.7.1.3. Compliance

The compliance with study medication will be assessed by comparing the amount of medication remaining at each visit with the amount predicted to remain if the patient is compliant with the prescription.

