5.2.9. T1 – Telephone contact (Day 59 ± 1 day)

This phone call between patients (or their parents) and the investigator (or his/her deputy) will

allow to record all adverse events having occurred since the latest visit (AE recorded at visit

V8), and to fill in the withdrawal symptoms questionnaire and ascertain that the treatment

discontinuation is well tolerated.

5.2.10. V8 - End of study visit or Start of Open-Label after 1 week of placebo wash out

(Day 63 ± 2 days) / Premature withdrawal visit (Double blind phase)

The premature withdrawal patients from the study should be followed by a visit performed

within a maximum of 5 days after the last dose of study drug.

A complete interrogation including occurred of possible adverse events and concomitant

medication used will be done and recorded,

A physical examination including vital signs shall be carried out,

12-lead ECG recording with calculation and control of QTcF,

A blood sample will be taken for routine haematological and biochemical test (including β-

HCG pregnancy test for pubescent female) and semi-quantitative urinalysis (dipstick), (only for

premature withdrawal patient),

The following questionnaires should be performed:

- PDSS,

- CASS,

- CDI,

- C-SSRS,

- Ullanlinna narcolepsy scale, (only for premature withdrawal patient),

- CGI-C on EDS and on cataplexy,

- Patient's Global Opinion on the effect of investigational treatment if able to express himself.

If not will be reported either by parents or teachers, (only for premature withdrawal patient),

- Retrieval of sleep diary and check by the investigator,

BIOPROJET Version 3.0 Protocol P11-06/ BF2.649 September 30th, 2020

EudraCT number: 2013-001506-29

-Withdrawal symptoms questionnaires.

The treatment pack bring back from previous visit by patient is checked by investigator for the

compliance.

Patients willing to continue the study in the prolonged open label period will receive a new

pack of investigational treatment and will start an escalating dose treatment. Week 1 at

5 mg/day then week 2 at 10 mg/day. Those patients will receive one sleep diary which have to

be filled out daily during the 7 days prior to the next visit. Patients not willing to continue in

the study will be followed under usual practice.

When a patient has already performed the visit V8, the follow up control visits will be scheduled

and an end of study visit should be planned as soon as the BF2.649 (pitolisant) is

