5.3.2. Type and timing of data to be collected from withdrawn patients

When a patient is prematurely withdrawn from the study before the "End of study visit" V8, the investigator has to perform a complete visit, within a maximum of 5 days after the last dose of study drug. This will also apply for open label phase.

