# Missing data handling:

Missing evaluations are not imputated.

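### The Patient's Global Opinion is collected at premature withdrawal, but the SAP scores it at V7 only, so the exploratory response comparison is in effect a V7-completer analysis

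*SAP*

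**What the plan says.** **Timing of the endpoint.** Protocol 3.3.2 lists "Patients' Global Opinion on treatment effect at the end of treatment if able to express" himself among the secondary endpoints, and the synopsis has the same item. SAP 3.1.2 repeats the end-of-treatment timing as an objective.

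**Collection.** Protocol 3.7.1.2.7 reads "At V7 and all visits of open-label period, patients' global opinion will be reported by patient". The double-blind schedule in the protocol and Table 1 of the SAP mark the PGO in two columns: V7 and premature withdrawal. Protocol 5.2.10 (V8 / premature withdrawal visit) limits collection at that slot to early stoppers: "If not will be reported either by parents or teachers, (only for premature withdrawal patient"). The synopsis agrees. Protocol 5.3.2 fixes the timing for a patient withdrawn before V8: "the investigator has to perform a complete visit, within a maximum of 5 days after the last dose of study drug".

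**Analysis.** SAP 4.5.3.3.7 turns the six-level opinion into a binary response (PGO-C, any improvement), and the definition is "This endpoint is defined as the value at V7 in the response to treatment (based on PGO-C"). The arms are compared at V7 with a chi-square test, and the p-value is set against 0.05. On missing data: "Missing evaluations are not imputated". SAP 4.1.4.1 limits imputation to UNS, PDSS, UNS-CTP, WRC and MWT. SAP 4.1.2 leaves missing responses out of percentage denominators. SAP 4.5.3 places all efficacy analyses in the FAS and the PPS.

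**Rank.** SAP 4.1.3.2 treats every endpoint outside the five-step fixed sequence as exploratory and supportive. The PGO is one of these.

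**The concern.** For a child who stops early, the opinion taken at the withdrawal visit is the end-of-treatment opinion. The protocol requires it and confines that slot to exactly these children, yet no rule in the SAP carries it into the endpoint. The child then counts in neither the numerator nor the denominator of the response rate.

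Stopping for lack of effect or poor tolerance is plausibly related to the opinion itself. If stopping differs between arms, a comparison among those who reached V7 can be distorted. The analysis is also labelled FAS while its actual denominator is smaller and depends on what happened after randomisation.

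**Working it through.** **Step 1. Does any rule bring the withdrawal-visit PGO into the endpoint?**

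| SAP place | Rule | Covers the withdrawal-visit PGO? |
|---|---|---|
| 4.5.3.3.7 | Endpoint and test use the V7 value | No |
| 4.1.5.1 | End value defined for UNS, PDSS and CASS, from V6 and V7 | No |
| 4.1.4.1 | Imputation for five endpoints only | No |
| 4.1.2 | Missing responses leave the denominator | No; removes the patient |
| 4.5.3.2.4 (MWT) | V7 or the last on-study visit | Other endpoint |
| 4.5.3.3.8 (withdrawal symptoms) | Premature withdrawal visit named | Other endpoint |

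No rule does. The SAP names a last or withdrawal visit for two other assessments and gives no reason for treating the PGO differently. One qualification: 4.5.3.3.7 also promises descriptive statistics of the levels by arm, in a sentence that does not repeat the V7 restriction. The exclusion is therefore certain only for the PGO-C comparison.

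**Step 2. How many patients?** The plan states no response rate, power or sample size for the PGO, so there is no figure of its own to reproduce. The only relevant count is in protocol 7.7.2: 25 of 27 randomised patients had V6 and V7 values.

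- Without those values: 2/27 = 7.4% (exact 95% CI 0.9% to 24.3%).
- Applied to 108 patients: 0.074 × 108 = 8 (about 1 to 26).

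The reason the two patients lacked values is not stated. They may not have been early stoppers.

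**Step 3. Illustration on assumed rates.** Assumed, not documented: V7 response of 65% on pitolisant and 40% on placebo, and 20% response among early stoppers in either arm. Planned sizes are 72 and 36. With *a* stoppers on pitolisant and *p* on placebo, the rates over all randomised patients are

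- pitolisant: [0.65(72 − a) + 0.20a]/72
- placebo: [0.40(36 − p) + 0.20p]/36

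The V7-only difference is 25.0 points. Its SE is √(0.65×0.35/72 + 0.40×0.60/36) = 0.099.

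| a / p | Pitolisant | Placebo | Difference | Shift from V7-only |
|---|---|---|---|---|
| 5 / 3 | 44.55/72 = 61.9% | 13.8/36 = 38.3% | 23.5 | −1.5 (0.15 SE) |
| 8 / 0 | 43.2/72 = 60.0% | 14.4/36 = 40.0% | 20.0 | −5.0 (0.5 SE) |
| 0 / 8 | 46.8/72 = 65.0% | 12.8/36 = 35.6% | 29.4 | +4.4 |

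The last row shows that the sign depends on which arm loses more patients.

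**Step 4. A harsher bound.** Here every early stopper counts as a non-responder (uncorrected chi-square, whole-number counts near the same V7 rates).

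| Stoppers, placebo / pitolisant | V7 only | All 108 |
|---|---|---|
| 3 / 5 | 13/33 v 44/67: 26.3 points, p = 0.013 | 13/36 v 44/72: 25.0 points, p = 0.014 |
| 1 / 7 | 14/35 v 42/65: 24.6 points, p = 0.018 | 14/36 v 42/72: 19.4 points, p = 0.057 |

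This is a bound because a recorded withdrawal-visit opinion could be favourable. Near balance, almost nothing changes. With marked imbalance, the p-value can cross 0.05.

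**The case against.** **The SAP follows the protocol's own section on this measure.** Protocol 3.7.1.2.7 names V7, SAP 4.5.3.3.7 takes over that text, and the protocol heads V7 as the end of the double-blind period. A reader might infer that the SAP departs from the protocol. The documents do not support that, because the protocol is not uniform. What stands is narrower: an assessment that both schedules require has no use in the comparison.

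**The rule is general.** All endpoints outside the five main ones go without imputation, and the End value for UNS, PDSS and CASS also ignores the withdrawal visit. This is true. However, UNS and PDSS have multiple imputation to cover early stoppers, and the PGO has nothing. The hypothetical strategy for discontinuation in SAP 4.5.3.1.1 is set for the primary endpoint. An unadjusted comparison of V7 completers would match it only if stopping were unrelated to the opinion within each arm.

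**Combining visits changes the question.** A withdrawal-visit opinion may come during titration, whereas V7 follows four weeks at a stable dose. This stands as a real cost, and it is the reason to keep the V7-only result alongside.

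**The bias is not shown.** This also stands. A reader might infer that the V7-only rule inflates the pitolisant response. No document gives stopping or response rates by arm, and if placebo children stop more often the rule can work against pitolisant.

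**Conclusion.** The point holds at low severity. As written, the PGO-C comparison covers only patients with a V7 opinion, although it is labelled as an FAS analysis and its objective is the opinion at the end of treatment. The recorded opinion of an early stopper does not enter it.

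The primary result, the fixed sequence and the type I error are unaffected, because the PGO is exploratory. The direction of bias is unknown. Its size is illustrative only: about 1.5 points with near-balanced stopping, and 4 to 5 points if all of about 8 stoppers are in one arm. Those figures rest on the assumed rates of 65%, 40% and 20%, and on carrying a count of 2 in 27, of unstated cause, over to 108 patients.

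**What to change.** In SAP 4.5.3.3.7:

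1. Define the endpoint as PGO-C at V7 or, for patients who stop before V7, at the premature withdrawal visit. Make the chi-square test refer to this value.
2. Keep the V7-only observed-case comparison as supportive.
3. Add a sensitivity analysis in the FAS that counts patients with neither value as not improved.
4. Report the number in each arm with a V7 value, a withdrawal-visit value and neither.

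The cost is SAP wording and a little programming; the schedule already requires the data. Opinions given at different times and doses will be combined, and the response rate may come out slightly less favourable.

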## Analyses:

The difference between placebo and BF2.649 will be studied at V7 using a Chi-2 test. In addition, descriptive statistics of levels by treatment group will be provided

# Missing data handling:

Missing evaluations are not imputated.

# Statistical elements:

For these comparisons the following elements will be provided in a summary table:

- Estimate (Standard Error) of the difference between the proportions of patients.
- Two-sided 95% CI of the estimate.
- P-value from Chi-2 test (to be compared to 0.05).

# 4.5.3.3.8 Withdrawal symptoms questionnaire (DSM IV)

A questionnaire is asked to patients about their feeling of any symptoms during the last week. Analyses:

Descriptive statistics at each visit (T1, V8 and eventually the premature withdrawal visit) by symptom by treatment group will be provided.

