- Investigational treatment allocation: No increase of pitolisant dosage will be authorized, the dose of pitolisant will be individually adjusted according to the assessment of investigators on the basis of efficacy, tolerance and weight,

Patients taking pitolisant 5 mg/d (or placebo) continue the same dose,

Patients taking pitolisant 10 mg/d (or placebo) continue the same dose or could reduce to pitolisant 5 mg/d (or placebo),

Patients taking pitolisant 20 mg/d (or placebo) continue the same dose or could reduce to pitolisant 10 mg/d (or placebo),

Patients taking pitolisant 40 mg/d (or placebo) continue the same dose or could reduce to pitolisant 20 mg/d (or placebo),

From this date onwards, no dosage change will be allowed. Beginning of the 4-week stable dose period.

V6 – Control treatment visit (D49 ± 2 days)

- A complete interrogation including control of the treatment compliance, count of remaining tablet and verification of the forgotten treatment intake.
- Adverse events and concomitant medication recording,
- A physical examination including vital signs shall be carried out,
- 12-lead ECG (QTcF value),
- The following questionnaires should be performed:
 - PDSS,
 - CASS.
 - CDI,
 - C-SSRS,
 - UNS.
 - TEA-Ch,
 - Clinical Global Impression of Change (CGI-C) on EDS and on cataplexy,
 - Retrieval of sleep diary of the previous visit and delivery of one other sleep diary which have to be completed every evening until the next visit.
- No dispensation performed at V6.

V7 - End of Double Blind Period (D56 ± 2 days)

- A complete interrogation including control of the treatment compliance, count of remaining tablets and verification of the forgotten treatment intake,
- Adverse events and concomitant medication recording,
- A physical examination including vital signs shall be carried out,
- 12-lead ECG (QTcF value),
- A blood sample will be taken for routine haematological and biochemical test (including β -HCG pregnancy test for pubescent female) and semi-quantitative urinalysis (dipstick),

A urine drug testing (for patients from 12 years),

- Maintenance of Wakefulness Test (MWT) (four sessions of 30-minute tests)
- The following questionnaires should be performed:
 - PDSS,
 - CASS,

- C-SSRS,
- UNS.
- CGI-C on EDS and on cataplexy,
- Retrieval of sleep diary of the previous visit and delivery of one other sleep diary which have to be completed every evening until the next visit.

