- 13) Active clinically significant illness, including unstable cardiovascular, endocrine, neoplastic, gastrointestinal, haematological, hepatic, immunologic, metabolic, neurological (other than narcolepsy/cataplexy), pulmonary, and/or renal disease which could interfere with the study conduct or counter-indicate the study treatments or place the patient at risk during the trial or compromise the study objectives.
- 14) Prior severe adverse reactions to CNS stimulants.
- 15) Known hypersensitivity to the tested treatment including active substance and excipients.
- 16) The inability to continue daily activities safely, without the use of treatment against EDS.
- 17) Any patient presenting congenital galactosemia, glucose-galactose malabsorption or lactase deficiency due to the presence of lactose in investigational treatments.
- 18) Patients participating in another study or being in a follow-up period for another study.
- 19) Cannot be contacted in case of emergency.

STUDY TREATMENT

Patients will be outpatients followed in ambulatory way during the whole study period and they will all receive the investigational study treatment pitolisant or placebo as described § 4.2. Patients will be asked to take the study drug every day before breakfast, according to the investigator's prescription regarding the dose regimen of patients, based on the product efficacy

and tolerance.

The total treatment duration of this double blind study is 8 weeks. Patients will start pitolisant treatment with escalating doses scheme on the first 4 weeks, as follows:

- V2 5 mg of BF2.649 or placebo / day during the first week,
 - 10 mg of BF2.649 or placebo /day during the second week,
- V3 Increase to 20 mg/d or maintain at 10 mg/d or reduce to 5 mg/d of BF2.649 (or placebo) per day for 7 days depending on efficacy and tolerability.

- V4 It will also be possible to reduce the dose administered to the patients, or to increase it without exceeding 40 mg/d. Patients with a weight less than 40kg could be treated with a maximum daily dose of 20mg.
- V5 It will be possible to reduce the dose administered to the patients, but not to increase it.
 - As from V5 onwards, no dosage change of the study treatment will be authorized.
- At the end of the double blind treatment (V7), the investigator will provide placebo to all patients for the one-week wash out period.

In open-label period patients will start pitolisant treatment with escalating doses scheme, as follows:

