3.7.1.2.5. Maintenance of Wakefulness Test 30-minute version

The Maintenance of Wakefulness Test (MWT) is used in this study to assess an individual's ability to maintain awake while resisting the pressure to fall asleep.

Patients will be administrated four 30-minute MWT sessions at 2-hour intervals at inclusion visit (V2) and at endpoint visit (V7 or the last on-study visit), according to validated standard [Doghramji K et al, Electroencephalogr Clin Neurophysiol. 1997; 103:554-62]8.

Patients will be required to have sufficient nocturnal sleep (minimum 6 hours) and not drink alcohol during the night prior to this visit. The patient will be required to take their morning treatment and a light breakfast before 8.00 a.m. and arrive in the trial center around 9.00 a.m.; lunch immediately after the termination of the second session. They should refrain from drinking any stimulatory beverage such as coffee, tea or Coca-Cola this morning until the end of this visit.

The first session begins at 10.00 a.m. Patients are required to recline comfortably in a quiet, dimly lit bedroom at ambient temperature (as close to 22°C as possible). Patients are instructed to remain awake for as long as possible. Sleep onset is defined by either 3 consecutive 30-s epochs of stage 1 sleep or any single 30-s epoch of stage 2, 3, 4 or REM sleep.

Each session is terminated either at the first unequivocal onset of sleep defined as above or, if sleep onset is not achieved, after maximum in-bed duration of 30 minutes. Polysomnographic recordings are made to determine sleep onset, and mean sleep latency is calculated (maximum score 30 minutes).

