3.7.2.7. Withdrawal symptoms

A specific questionnaire provided 1 week after discontinuation of the study drug will investigate

Confidential

63

Version 3.0 September 30th, 2020

the possible occurrence and pattern of amphetamine like withdrawal symptoms (DSM-IV) which are defined as dysphoria and two or more of the following symptoms: fatigue, vivid and unpleasant dreams, insomnia or hypersomnia, increased appetite and psychomotor retardation or agitation.

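### With a one-week recall, the withdrawal questionnaire at T1 and at premature withdrawal covers days on treatment as well as days off it, so those tables cannot by themselves isolate withdrawal symptoms

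*SAP*

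**What the plan says.** The SAP describes the questionnaire in one sentence (4.5.3.3.8): "A questionnaire is asked to patients about their feeling of any symptoms during the last week". The next sentence sets the analysis: "Descriptive statistics at each visit (T1, V8 and eventually the premature withdrawal visit) by symptom by treatment group will be provided". No separate recall period is given for any of the three occasions.

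Protocol 3.3.2 lists a comparison of the two groups on the "Withdrawal symptoms questionnaire (DSM IV) on D59 during a phone call (T1") and again at V8 on D63. Protocol 3.7.2 also lists withdrawal symptoms among the safety criteria. Protocol 3.7.2.7 describes the timing differently: "A specific questionnaire provided 1 week after discontinuation of the study drug will investigate" amphetamine-like withdrawal symptoms, defined as dysphoria plus at least two others from a list that includes fatigue and insomnia or hypersomnia.

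The visit timing is in the Synopsis (study design and conduct): "V7 - End of Double Blind Period (D56 ± 2 days") and "T1 - Telephone contact at D59 (± 1 day"). V8 is D63 ± 2. The protocol's study treatment section states when blinded drug ends: "At the end of the double blind treatment (V7), the investigator will provide placebo to all patients for the one-week wash out period". The premature withdrawal visit is due at most 5 days after the last dose. The schedules in both documents show no withdrawal questionnaire at V7 or earlier.

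**The concern.** A withdrawal questionnaire is informative when the period it asks about begins at the stop. Here the call comes about three days after the switch to placebo, while the question reaches back seven. A symptom reported at T1 may have been present on treatment, after it, or both, and the answer does not say which.

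This matters because the same symptom can arise on either side of the stop. Insomnia is on the protocol's list of withdrawal symptoms (3.7.2.7), and it is also one of the most common adverse events on pitolisant, at 9.3% (Protocol 1.3). Insomnia on active drug could appear in the T1 column of the pitolisant arm as though it followed stopping. The placebo arm does not correct for this, because the effect would be specific to the drug. In the other direction, a symptom that begins only after stopping is asked about over a window consisting largely of on-drug days. At stake is the reading of withdrawal safety in children, not any efficacy conclusion.

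**Working it through.** **Inputs**
- Recall length: 7 days (SAP 4.5.3.3.8).
- V7: D54 to D58. T1: D58 to D60. V8: D61 to D65 (Protocol Synopsis and schedule).
- Premature withdrawal visit: 0 to 5 days after the last dose (Protocol schedule, note 3).
- The V7 day counts as on treatment. The instructions for the wakefulness test, which is done at V2 and V7, say "The patient will be required to take their morning treatment and a light breakfast before 8.00 a.m" (Protocol 3.7.1.2.5).

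**Formula.** Gap = questionnaire day − V7 day. Recalled days on treatment = max(0, 7 − gap).

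**The plan's own figure.** Protocol 3.7.2.7 gives one week after discontinuation.
- V8: 63 − 56 = 7 days. Reproduced.
- T1: 59 − 56 = 3 days. Not reproduced.
- Premature withdrawal: 0 to 5 days. Not reproduced.

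**T1 at nominal timing.** 7 − 3 = 4 days on treatment, and 4/7 = 57%. By calendar, a week that includes the call day is D53 to D59, with D53 to D56 on treatment (4 days). A week that excludes the call day is D52 to D58, with D52 to D56 on treatment (5 days).

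**T1 over all permitted day pairs** (recalled days on treatment, of 7):

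| V7 day | T1 on D58 | T1 on D59 | T1 on D60 |
|---|---|---|---|
| D54 | 3 | 2 | 1 |
| D55 | 4 | 3 | 2 |
| D56 | 5 | 4 | 3 |
| D57 | 6 | 5 | 4 |
| D58 | 7 | 6 | 5 |

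The range is 1 to 7, so no permitted pair gives a recall week wholly off drug. A majority (4 or more) is on treatment in 0 + 1 + 2 + 3 + 3 = 9 of 15 pairs.

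**V8.** The gap runs from 61 − 58 = 3 to 65 − 54 = 11 days, and is 7 at nominal timing, which leaves 0 days on treatment. Pairs with a gap under 7 days, for V7 on D54 to D58 in turn: 0 + 1 + 2 + 3 + 4 = 10 of 25. Only one pair (V7 on D58, V8 on D61) has a majority on treatment: 7 − 3 = 4.

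**Premature withdrawal during the double-blind period.** 7 − 5 = 2 up to 7 − 0 = 7 of the recalled days precede the stop.

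**Would timing T1 from the last dose be enough?** With T1 at last dose + 3 ± 1 days and the recall unchanged, the days on treatment are 7 − 4 = 3 to 7 − 2 = 5, and 4 at nominal timing. The recall wording is the main cause.

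**The case against.** The strongest reply has four parts.

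1. **The form is not available.** The questionnaire is not among the protocol's appendices, so the one-week recall at T1 rests on one general SAP sentence. The T1 form may be worded differently. This stands as a limit on certainty, but the SAP sentence is the only specification and it makes no exception for T1.

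2. **The weight is small.** SAP 4.1.3.2 treats everything outside the five tested endpoints as exploratory and supportive, and this table is descriptive, by visit and by symptom. V8 is reported separately and nominally covers a clean off-drug week. This stands, and it limits the importance of the point.

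3. **Other data help.** The T1 call also records adverse events since the last visit (Protocol 5.2.9), and these carry an onset or worsening date (SAP 4.5.4.1). PDSS and CASS are taken at V7 and V8, and the diary runs every evening to V8. A reader might therefore go too far in inferring that T1 says nothing about withdrawal. The documents do not support that: reported events can be dated. The help is partial, because a symptom ticked on the questionnaire need not have been reported as an adverse event.

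4. **The definition is demanding.** Withdrawal requires dysphoria plus two or more symptoms, so insomnia alone would not meet it. This is true, but the SAP tabulates individual symptoms and states no rule for applying the definition.

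A reader might also infer that the fault lies in windows counted from D0. No sentence states the anchor; it is only suggested by the day numbering, and other text ties the placebo week and V8 to V7. The extreme case, V7 and T1 both on D58, is formally allowed but unlikely in practice.

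**Conclusion.** The point holds in a limited form. As specified, the T1 and premature-withdrawal tables mix symptoms from before and after the stop and cannot by themselves separate them. At T1 the mixture is 4 of 7 days on treatment at nominal timing and 1 to 7 across the permitted windows; at premature withdrawal it is at least 2 of 7. V8 is sound at nominal timing but not for every permitted pair. Protocol 3.7.2.7 and 3.3.2 disagree on when the questionnaire is given.

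This rests on the SAP's recall sentence applying to all three occasions and on the V7 morning dose being blinded drug. If the last blinded dose were the day before V7, each count above zero would fall by one and a single T1 pair (D54 with D60) would become clean. The pair counts describe what the windows permit; they are not probabilities, since the documents give no distribution of actual visit days.

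A reader might infer that the trial has no usable withdrawal assessment or that a confirmatory result is affected. Neither follows: V8 provides a reading, and no tested endpoint or type I error statement depends on this questionnaire.

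**What to change.** **Preferred.** Word the recall at T1, V8 and premature withdrawal as *since the last double-blind dose (V7)*, with the patient's own last-dose date at premature withdrawal. That leaves no on-treatment days at any gap, so the T1 window need not move. The cost is a form change during a running trial, which mixes two recall definitions; results should then be shown by form version.

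**If the form cannot change**, amend SAP 4.5.3.3.8 to:
- report days since the last double-blind dose with each questionnaire, using the last-intake date over V2–V7 already derived in SAP 4.1.5.2;
- label T1 and premature-withdrawal results as mixed on/off-drug recall;
- use V8 with a gap of at least 7 days as the main withdrawal reading, and flag shorter gaps.

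This needs no new data and only a little more reporting.

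**In either case**, reconcile Protocol 3.7.2.7 with 3.3.2 on when the questionnaire is given, and state the recall period for each occasion. An extra questionnaire at V7 is not needed for this purpose.
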